Study treatment should be administered by the patient once per day. Following enrollment (Visit 3/Day 1) patients will return to the site at 2 week intervals until Visit 5 (Month 1). Thereafter, scheduled visits will be monthly (please refer Table 7-1 for study visit evaluation schedule). Patients may return to the study center more frequently at the physician's discretion as clinically indicated or as per standard of care. Serious adverse events (SAEs) will be reported to the Novartis safety database within 24 hours of investigator or treating physician's knowledge of the event from the time the patient has signed informed consent until at least 30 days after the patient stopped study treatment. All other assessments are performed as per standard of care at the site and will not be captured in the eCRF.

Patients who discontinue study treatment before completing the study should be scheduled for a visit within 7 days after the last dose, at which time all of the assessments listed for the end of treatment (EOT) visit (i.e. Month 24). The planned duration of treatment in this study is for a maximum of 24 months.

[figure not shown]

Figure 4-1 Study design

DT = Dispensible tablet FCT = Film-coated tablet EOT = End of treatment

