7.1 Study flow and visit schedule

Table 7-1 lists all of the assessments and indicates with an "X", the visits when they are performed.

Patients should be seen for all visits to perform the scheduled assessments on the designated day, or as close to is as possible, i.e., not exceeding \pm 7 days. In this clinical trial, a week is 7 calendar days. Visits should be planned respective to Visit 3, rather than in relation to the previous visits.

All data obtained from these assessments must be supported in each patient's source documentation. No eCRF will be used as a source document. The table indicates which data are entered into the database (D) or remain in source documents only (S) (column category).

Table 7-1 Visit evaluation schedule

	Category	Protocol section	Screening	(z visits > 1week apart)¹							Tr	eatme	ent Pe	riod						End of Treatment	Safety Follow- up
Visit no.			1	2	3	4	5	6	7	8	9	10	11	12	13	14	15	16	17 to 27	28²	
Study month			-2	2W	D1	W2	M1	M2	М3	M4	М5	М6	М7	M8	M9	M10	M11	M12	M13 to M23	M24 or Within 7 days of last dose	30 days after last dose
Informed consent	(D)	7.1.1	Х																		
Inclusion/ exclusion criteria	(D)	7.1.1.1	Χ	Х																	
History of disease	(D)	7.1.1.3	Χ																		
Demography	(D)	7.1.1.3	Χ																		
Relevant medical history/current medical conditions	(D)	7.1.1.3	X																		
Prior chelation therapy	(D)	7.1.1.3	Х																		
Transfusion/RBC History	(D)	7.1.1.3	Х																		
Transfusions received	(D)	7.1.3	Х		Х	Х	Х	Х	Х	Х	Х	Х	Х	Х	Х	Х	Χ	Χ	Х	Х	
Physical exam	(S)	7.2.2.1	Х		Х	Χ	Х	Х	Х	Х	Х	Х	Х	Х	Х	Χ	Χ	Χ		Х	
Weight ³	(D)	7.2.2.3	Х		Χ	Χ	Х	Χ	Χ	Х	Х	Х	Х	Χ	Χ	Χ	Χ	Χ	Χ	Х	
Height	(D)	7.2.2.3	Х																		
Vital signs	(D)	7.2.2.2	Х	Х	Χ	Х	Х	Х	Х	Х	Х	Х	Х	Χ	Χ	Χ	Χ	Χ	Χ	Х	
Ocular exam⁴	(D)	7.2.2.4	Х															Χ		Х	
Audiometry ⁴	(D)	7.2.2.4	Х															Χ		Х	
ECG	(D)	7.2.2.7.1	Х															Х		Х	
Chest X-ray (if clinically indicated) ⁵	(D)	7.2.2.6	Х																		

	Category	Protocol section	Screening	apart)¹							Tı	eatme	ent Pe	riod						End of Treatment	Safety Follow- up
Visit no.		_	1	2	3	4	5	6	7	8	9	10	11	12	13	14	15	16	17 to 27	28 ²	
Study month			-2	2W	D1	W2	M1	M2	М3	M4	M5	М6	М7	M8	М9	M10	M11	M12	M13 to M23	M24 or Within 7 days of last dose	30 days after last dose
Prior and Concomitant medications	(D)	6.4	Х	х	х	х	Х	Х	Х	Х	Х	Х	Х	Х	Х	Х	х	Х	Х	Х	
Adverse events	(D)	7.2.2	Х	Х	Х	Χ	Х	Х	Х	Х	Х	Х	Х	Х	X	Χ	Х	Х	Х	Х	Х
Laboratory assessments ⁶ -Blood																					

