[Month 22 to Month 23]	Study Day 617 to Study Day 644	88 to < 92 weeks
[Month 23 to Month 24]	Study Day 645 to Study Day 672	92 to < 96 weeks
[Month 24 to Month 25]	Study Day 673 to Study Day 700	96 to < 100 weeks
[Month 25 to Month 26]	Study Day 701 to Study Day 728	100 to < 104 weeks
[Month 26 to Month 27]	Study Day 729 to Study Day 756	104 to < 108 weeks
[Month 27 to EOT]	Study Day ≥ 757	≥ 108 weeks

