2.3.3.2 Laboratory data and vital signs

Laboratory data (biochemistry, hematology, and urinary parameters as well as serum creatinine, creatinine clearance, and proteinuria) and vital signs will be collected at screening visits, regular patient visits, and EOT.

If two or more assessments are performed within a time window then the assessment closest to the planned visit will be used in analyses by time window. When two values are equidistant from the planned assessment, the later one will be used in analyses.

Note: For worst post-baseline assessment, all on-treatment values are considered regardless of time windows. Table 2-2 shows the defined time windows, where a month is regarded as 4 weeks.

Table 2-2 Time windows for laboratory and vital signs data

Time window	Planned visit timing	Time window definition
On-treatment		
Baseline	On or before Study Day 1*	≤ Study Day 1*
Week 2	Study Day 15	Study Day 2 to Study Day 21
Month 1	Study Day 29	Study Day 22 to Study Day 43
Month 2	Study Day 57	Study Day 44 to Study Day 71
Month 3	Study Day 85	Study Day 72 to Study Day 99
Month 4	Study Day 113	Study Day 100 to Study Day 127
Month 5	Study Day 141	Study Day 128 to Study Day 155
Month 6	Study Day 169	Study Day 156 to Study Day 183
Month 7	Study Day 197	Study Day 184 to Study Day 211
Month 8	Study Day 225	Study Day 212 to Study Day 239
Month 9	Study Day 253	Study Day 240 to Study Day 267

Time window	Planned visit timing	Time window definition
Month 10	Study Day 281	Study Day 268 to Study Day 295
Month 11	Study Day 309	Study Day 296 to Study Day 323
Month 12	Study Day 337	Study Day 324 to Study Day 351
Month 13	Study Day 365	Study Day 352 to Study Day 379
Month 14	Study Day 393	Study Day 380 to Study Day 407
Month 15	Study Day 421	Study Day 408 to Study Day 435
Month 16	Study Day 449	Study Day 436 to Study Day 463
Month 17	Study Day 477	Study Day 464 to Study Day 491
Month 18	Study Day 505	Study Day 492 to Study Day 519
Month 19	Study Day 533	Study Day 520 to Study Day 547
Month 20	Study Day 561	Study Day 548 to Study Day 575
Month 21	Study Day 589	Study Day 576 to Study Day 603
Month 22	Study Day 617	Study Day 604 to Study Day 631
Month 23	Study Day 645	Study Day 632 to Study Day 659
Month 24	Study Day 673	Study Day 660 to Study Day 687
Month 25	Study Day 701	Study Day 688 to Study Day 715
Month 26	Study Day 729	Study Day 716 to Study Day 743
Month 27	Study Day 757	Study Day 744 to Study Day 771
Month 28	Study Day 785	≥ Study Day 772
EOT		

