2.6.1 Primary endpoint

The primary variables are:

- treatment emergent AEs (TEAEs)
 - An AE is defined as treatment emergent if its onset date is on or after (≥) the first administration of study treatment within this study or events present prior to start of study treatment but increased in severity on or after (≥) the first administration of study treatment within this study but not later than 30 days after the last study treatment in this study (i.e. during the safety observation period, see Section 2.1 for definition).
- changes from baseline at Months 6 and 12 for the following laboratory assessments:
 - serum creatinine
 - creatinine clearance
 - ALT/SGPT
 - AST/SGOT
 - red blood cell (RBC)
 - platelets

• white blood cell (WBC)

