2.6.2 Statistical hypothesis, model, and method of analysis

No hypotheses will be tested. All analyses will be descriptive in nature.

The incidence of any TEAEs overall and by severity will be summarized using frequency counts, percentages of patients, and 95% CIs for percentages obtained using Clopper-Pearson method.

Laboratory data will be summarized using descriptive statistics including 95% CI of the mean for raw values and absolute change from baseline at each visit (see Table 2-2 for time windows definition). Furthermore, mean and standard error (SE) values will be plotted over time (see Table 2-2 for time windows definition) for each of the laboratory parameters of interest (serum creatinine, creatinine clearance, ALT/SGPT, AST/SGOT, RBC, platelets, WBC total).

The analysis of the primary variables will be performed on the Safety Set.

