2.8.1 Secondary endpoints

The secondary variables are:

- serum ferritin level at baseline, Month 6 (Visit 10), and Month 12 (Visit 16)
- change from baseline in serum ferritin at Month 6 (Visit 10) and Month 12 (Visit 16)

It should be noted that the maximum serum ferritin provided by certain laboratories is 4500 ng/mL with values above 4500 ng/mL represented as ">4500". If there is an occurrence of ">4500", the site will record this value in the electronic data capture (EDC) system as 4500 ng/mL. For derivations and table summaries, the value of 4501 will be used; for listings this value will be shown as ">4500".

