2.8.2 Statistical hypothesis, model, and method of analysis

No hypotheses will be tested. All analyses will be descriptive in nature.

Serum ferritin will be summarized using descriptive statistics of raw values, absolute change from baseline, and relative change from baseline at each visit (see Table 2-2 for time windows definition). The summaries will include n, mean with respective 95% CI, SD, minimum, Q1, median, Q3, and maximum.

The analysis of the secondary variables will be performed on the FAS.

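### SAP 2.8.1 ties Months 6 and 12 to Visits 10 and 16, but Table 2-2 fills those rows from 4-week windows; unless visits were about 28 days apart, the Month 12 row shows the wrong visit

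*SAP*

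**What the plan says.** - **Time points by visit.** SAP 2.8.1 lists as a secondary variable "change from baseline in serum ferritin at Month 6 (Visit 10) and Month 12 (Visit 16". Protocol Table 7-1 has the same pairing: Visit 10 is M6 and Visit 16 is M12.
- **Primary laboratory variables.** SAP 2.6.1 lists "changes from baseline at Months 6 and 12 for the following laboratory assessments": creatinine, creatinine clearance, ALT, AST, RBC, platelets and WBC.
- **Rows by study-day window.** SAP 2.6.2 summarises the laboratory data as "raw values and absolute change from baseline at each visit (see Table 2-2 for time windows definition". SAP 2.8.2 does the same for ferritin, including "relative change from baseline at each visit (see Table 2-2 for time windows definition".
- **The windows.** SAP 2.3.3.2: "Table 2-2 shows the defined time windows, where a month is regarded as 4 weeks". Month 6 is Days 156–183, Month 12 is Days 324–351 and Month 13 is Days 352–379.
- **The booking rule.** Protocol 4.1 says that "patients will return to the site at 2 week intervals until Visit 5 (Month 1"), with monthly visits afterwards. Protocol 7.1 plans visits from Visit 3 with a ±7-day tolerance. It states "In this clinical trial, a week is 7 calendar days" but gives no length for a month. Protocol 6.1.5 and 7.1.3 cap treatment at 24 months.

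**The concern.** The SAP has two rules for what belongs in the Month 6 and Month 12 rows and does not say which prevails. They give the same answer only if sites booked visits about every 28 days. In ordinary use, monthly visits over 24 months could equally mean calendar months or 30-day steps, and the gap grows with each visit.

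Months 6 and 12 are the named time points for the primary laboratory variables and for serum ferritin. If the windows are out of step with the booking, the report's Month 12 row holds the Month 11 visit, and a reader could not tell this from the table. Table 7-1, as extracted, marks hematology and biochemistry up to Visit 16 and again at Visit 28, but not at Visits 17–27. For ALT, AST, RBC, platelets and WBC the Month 12 sample would then sit alone in a Month 13 row for which nothing is scheduled. Protocol 7.2.2.5.1 and 7.2.2.5.2 say these samples are taken at every visit while pointing to that table, so this last consequence is less certain. Ferritin, creatinine and creatinine clearance are marked monthly throughout.

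**Working it through.** **1. Reproduce Table 2-2.** With Day 1 as first dose (SAP 2.1), the planned day of Month m is 28m + 1, and from Month 2 to Month 27 the window runs from 13 days before to 14 days after it.
- Month 6: 28 × 6 + 1 = 169, window 156–183.
- Month 12: 28 × 12 + 1 = 337, window 324–351.
- Month 13: 28 × 13 + 1 = 365, window 352–379.

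All match the table.

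**2. Spacing at which the two rules agree.** For a constant spacing of s days from Day 1, Visit 10 is planned on Day 1 + 6s and Visit 16 on Day 1 + 12s, each ±7.
- Visit 16 in Month 12 over the full tolerance: (324 − 1 + 7)/12 = 27.5 to (351 − 1 − 7)/12 = 28.58 days. Planned day alone: 323/12 = 26.9 to 350/12 = 29.17.
- Visit 10 in Month 6 over the full tolerance: (156 − 1 + 7)/6 = 27.0 to (183 − 1 − 7)/6 = 29.17. Planned day alone: 155/6 = 25.8 to 182/6 = 30.3.
- Both visits together: 27.5 to 28.6 days.
- Visit 16 always in Month 13: (352 − 1 + 7)/12 = 29.83 to (379 − 1 − 7)/12 = 30.92.

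**3. Place the visits under four booking rules.** Calendar booking was run over all 1,461 start dates from 2016 to 2019. Shares assume attendance uniform over the 15 tolerance days.

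| Booking | Visit 16 (±7) | Row | Visit 15 in Month 12 row | Visit 10 in Month 7 row |
|---|---|---|---|---|
| 28 days | 330–344 | Month 12, 100% | 0% | 0% |
| 30 days from Day 1 | 354–368 | Month 13, 100% | 15/15 = 100% | 5/15 = 33% |
| 30-day steps from Day 29 | 352–366 | Month 13, 100% | 13/15 = 87% | 3/15 = 20% |
| Calendar months | 359–374 | Month 13, 100% | 100% | 40–60% by start date, 51% on average |

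Under calendar booking Visit 10 is planned on Days 182–185, which straddles the 183/184 cut-off. With attendance exactly on the planned day it is therefore all or none for a given start date. Under 30-day booking exact attendance (Day 181) keeps it in Month 6.

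**4. Patients with no Month 6 value.** Visit 9 can fall in the Month 6 window as well. With 30-day booking, Visit 9 (Days 144–158) misses that window on 12 of 15 days and Visit 10 on 5 of 15. If the two are independent, 12/15 × 5/15 = 27% of patients who attend both visits have no Month 6 value. With calendar booking the figure is 33% on average (24–36% by start date). SAP 2.8.3 imputes nothing, and SAP 2.1 requires a value at the visit for a change from baseline.

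**5. What the later rows show.** With 28-day booking Visit 28 is Day 673, at latest 680, and the on-treatment tail ends by 680 + 30 = Day 710. The Month 26 row of Table 2-2 (Days 716–743) cannot then be reached on schedule. With calendar booking Visit 28 is Day 731 or 732, range 724–739, which is inside that row. The tail ends by 739 + 30 = 769, short of Day 772, where Month 28 starts. Table 2-1 counts exposure and has no tail, so its last row, "Month 27 to EOT" (Day 757 onward), is also out of reach on schedule under either rule.

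**The case against.** The strongest reply is that the defect depends on a booking rule that neither document states. The SAP defines its month as 4 weeks for both tables, Table 2-2 gives Month 12 a planned timing of Day 337, and the protocol reaches Visit 5 (Month 1) by two 2-week steps, that is, Day 29. Read that way, the two rules agree. This stands, and it makes the point conditional.

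A reader might infer from the rows running past Month 24 that sites must have booked by calendar month. The documents do not support that. The last row of each table is an overflow row that neither schedule reaches. The middle rows, such as Month 26, make longer months plausible, but spare rows for late visits would explain them too.

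Three further limits also stand. Visit 10 taken alone is more forgiving, since its planned day stays in Month 6 up to 30.3-day spacing. The statement about every Visit 16 covers only visits within ±7 days. And no hypothesis is tested and every row is tabulated, so a shifted Visit 16 value appears one row later and is not lost.

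That does not remove the problem. In a descriptive study these by-visit tables are the laboratory and ferritin result, and Months 6 and 12 are the rows the plan names.

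**Conclusion.** The SAP's visit-based and window-based definitions of Months 6 and 12 conflict unless visits were about 27.5 to 28.6 days apart, and the protocol does not fix the interval. With calendar or 30-day booking, all in-tolerance Visit 16 values move to the Month 13 row, 87–100% of Visit 15 values land in the Month 12 row, and roughly 20–60% of Visit 10 values move to Month 7. With 28-day booking there is no shift. The Visit 10 shares and the 27–33% without a Month 6 value assume uniform attendance within ±7 days; the trial's own figures depend on enrolment and visit dates that are not given.

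It would be tempting to say that the Month 12 results are wrong. The documents support only that they will be mislabelled if booking was not near 28 days. Overall adverse event tables, worst-value shift tables and the EOT row are unaffected. This should be fixed because the check is cheap and the rows are the named ones.

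**What to change.** Before database lock, compare actual visit dates with Table 2-2. If the spacing is about 28 days, state that interval in the SAP. If it is not, take one of two routes.

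1. **Re-centre the windows** after Month 1 on the observed interval, keeping Week 2 at Day 15 and Month 1 at Day 29. For 30-day booking, Month 6 becomes Days 167–196 and Month 12 Days 347–376; for calendar booking, Days 169–199 and 352–381. With windows built this way, none of 504,045 simulated visit-days (1,461 start dates × 23 visits from Month 2 to Month 24 × 15 tolerance days) was misplaced, for either booking rule. Apply them to everything that cites Table 2-2: laboratory data, ferritin, vital signs, transfusions, hepatitis data by visit, unscheduled values and early EOT values.
2. **Assign scheduled values by nominal visit**, as SAP 2.8.1 already implies, and use the same re-centred windows for unscheduled and early EOT values. Do not label an early EOT value as Month 24, although Protocol 7.1.4 gives that visit the Month 24 name.

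Under either route, label the Table 2-1 periods in weeks only.

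The cost is one added derivation step and no new data. The second route has one side effect: because SAP 2.3.3.2 takes the value closest to the planned day, a row could change even at 28-day spacing where an unscheduled value lay closer than the scheduled one.

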2.4 Patient disposition, demographics and other baselinecharacteristics

Patient disposition, background and demographic characteristics will be reported for the FAS, unless otherwise specified.

No inferential tests for differences in background and demographic characteristics will be performed.

2.4.1 Patient disposition

The number of patients screened will be summarized by country and center.

The number and percentage (based on the number of patients in the FAS) of patients who complete the study will be displayed. The primary reason for premature study discontinuation will also be displayed.

The total number of patients screened and the number of patients screened, but did not start treatment will be shown. The primary reason for screening failure will be summarized.

All patient disposition data will be listed by center and patient number for the FAS.

2.4.2 Background and demographic characteristics

Demographic, background data and key efficacy variables at baseline will be summarized for the FAS.

The time since diagnosis of disease will be derived using the following formula:

Time since diagnosis (years) = (Date of informed consent – Date of diagnosis) $\frac{1}{365.25}$

Demographics

Categorical variables

- age ($< 18, 18 \text{ to } < 50, 50 \text{ to } < 65, \ge 65 \text{ years}$)
- child bearing potential (Able to bear children, Premenarche, Post menopausal, Sterile of child bearing age)
 - Note: Child bearing potential will only be completed for patients where gender is marked as female.
- ethnicity (Hispanic/Latino, Chinese, Indian [Indian subcontinent], Japanese, Other)
- sex (Male, Female)
- predominant race (Caucasian, Black, Asian, Native American, Pacific Islander, Other)
- weight ($< 20, 20 \text{ to } < 35, 35 \text{ to } < 55, 55 \text{ to } < 75, <math>\ge 75 \text{ kg}$)

Continuous variables

- age (years)
- height (cm)
- weight (kg)
- body mass index (BMI) (kg/m²)

Disease characteristics

Categorical variables

- hepatitis B surface antigen (HBsAg) (Negative, Positive, Indeterminate/Borderline)
- hepatitis B surface antibody (HBsAb) (Negative, Positive, Indeterminate/Borderline)
- hepatitis C virus (HCV) antibody positive (Negative, Positive, Indeterminate/Borderline, Below detectable limit)
- HCV RNA positive (Negative, Positive, Indeterminate/Borderline, Below detectable limit)
- hepatitis status (Hepatitis B, Hepatitis C, Hepatitis B and C, No Hepatitis)
 - Hepatitis B is defined as HBsAg in the absence of HBsAb (i.e. HBsAg is positive and HBsAb is negative). HBsAg and HBsAb must be measured from the same sample, otherwise Hepatitis B status cannot be determined.
 - Hepatitis C is defined as HCV antibody positive with HCV RNA positive. HCV antibody positive and HCV RNA positive must be measured from the same sample, otherwise Hepatitis C status cannot be determined.

- Note: If there is no confirmatory assessment of HCV RNA measured from the same sample as HCV antibody, then the status of Hepatitis C will be regarded as Unknown/Undetermined.
- hematologically stable since last bone marrow examination (Yes, No)
- history of ICT (Yes, No)
- history of splenectomy (Yes, No)
 - Note: Patients with history of splenectomy are defined as those patients with a splenectomy recorded before Visit 3 (Day 1) (started before first administration of study treatment) in Relevant medical history/Current medical conditions eCRF (Preferred term [PT]: Splenectomy).
- main underlying disease (MDS with very low risk as per the Revised International Prognostic Scoring System [IPSS-R], MDS with low risk as per the IPSS-R, MDS with intermediate risk as per the IPSS-R, Thalassemia)
- formulation of the ICT received during CICL670F2201 (DFX DT, DFX FCT)
- type of last ICT prior to the study (Deferoxamine, Deferiprone, Combination therapy of Deferoxamine and Deferiprone, DFX, Combination therapy of Deferoxamine and DFX, Combination therapy of DFX and Deferiprone, Other)

Continuous variables

- time since diagnosis (years)
- time since last bone marrow examination (years)
- time since last blood transfusion (days)
- total number of blood transfusions received since last 12 months

Hepatitis data (HBsAg, HBsAb, HCV antibody positive, HCV RNA positive, Hepatitis status) will also be summarized by visit (see Table 2-2 for time windows definition). Hepatitis status was planned to be determined at Visit 3 (Day 1) however there is an option if some information was not collected then this can be collected at a later time-point.

Baseline abnormalities in ECG, audiometric test, and ocular exam

Categorical variables

- clinically significant abnormality in ECG (Yes, No)
- overall interpretation in audiometric test (Normal, Clinically insignificant abnormality, Clinically significant abnormality)
- overall interpretation in ocular exam (Normal, Clinically insignificant abnormality, Clinically significant abnormality)

Baseline laboratory values

Categorical variables

• Alanine aminotransferase (ALT)/serum glutamic pyruvic transaminase (SGPT) (≤ Upper limit of normal range (ULN), > ULN to 5×ULN, > 5×ULN)

- Aspartate aminotransferase (AST)/serum glutamic oxaloacetic transaminase (SGOT) (≤ ULN, > ULN to 5×ULN, > 5×ULN)
- Serum creatinine (\leq ULN, > ULN)
- Creatinine clearance ($< 40, 40 \text{ to } < 60, \ge 60 \text{ mL/min}$)
- Urine protein/creatinine ratio (UPC) (≤ 0.2 , > 0.2 to ≤ 1.0 , > 1.0 mg/mg)

Continuous variables

- ALT/SGPT (U/L)
- AST/SGOT (U/L)
- Serum creatinine (umol/L)
- Creatinine clearance (mL/min)
- UPC (mg/mg)

All demographic and baseline data will be listed by center and patient number for the FAS.

